8.5 Prohibited concomitant therapy

- Any treatment responsible for lymphocyte depletion and live-attenuated vaccines are not permitted
- Antineoplastic systemic chemotherapy or biological therapy
- This list is not comprehensive and is only meant to be used as a guide:
 - Herbal medications/preparations (except for vitamins). Herbal medications include, but not limited to: St. John's wort, Kava, ephedra (ma huang), ginkgo biloba, dehydroepiandrosterone (DHEA), yohimbe, saw palmetto, black cohosh, mistletoe and ginseng. Patients should stop using all herbal medications at least 7 days prior to first dose of study treatment.
 - Other investigational and antineoplastic therapies
 - Anti-arrhythmic therapy other than beta blockers or digoxin
 - Systemic corticosteroid therapy at a daily dose higher than 15 mg prednisone or equivalent. Previous corticosteroid therapy must be stopped or reduced to the allowed

dose at least 7 days prior to the screening CT/MRI). If a patient is on chronic corticosteroid therapy, corticosteroids should be de-escalated to the maximum allowed dose before the screening. Patients may be using topical or inhaled corticosteroids. Short-term systemic corticosteroids above 15 mg prednisolone or equivalent will be allowed. The use of corticosteroids as antiemetics prior to Pembrolizumab administration will not be allowed

- Ongoing immunosuppressive therapy
- Concomitant radiotherapy (it is assumed that radiation would be indicated only in case of progression, when the patient would come off study medication anyway)
- Medications or vaccinations specifically prohibited in the exclusion criteria are not allowed during therapy.

The therapies listed above are not prohibited anymore 110 days after last study drug administration (based on five times the terminal elimination half-life of Rituximab and Pembrolizumab). In case of disease progression the patient can receive a new anti-lymphoma treatment before this time period, the decision is at the discretion of the treating physician.

8.6 Vaccinations

- Immunizations status of eligible patients must be checked at the inclusion. National recommendations for adult immunization policy must be fulfilled before Rituximab delivery.
- Pneumococcal and hemophilus B vaccines are recommended in the absence of contraindications before Rituximab therapy. The interval of time between any immunization and the first Rituximab delivery should be at least of 28 days.

9. Schedule of assessments

9.1 Definition of (staging) examinations

9.1.1 Pathological diagnostic

Tissue diagnostic procedures must be performed within 12 months prior to study entry and have to include diagnostics by a reference pathology center. Biopsy material from an excisional or core biopsy must be submitted for retrospective central confirmation. Tissue samples dated > 12 months prior to informed consent can be accepted only if tissue material is available for retrospective confirmation, if there is no clinical indication for transformation of disease, and if the request for additional biopsy would be unethical treatment of the patient.

A local pathological diagnosis of MZL is obligatory before registration into the clinical trial. In addition, a reference pathological confirmation of the diagnosis MZL has to be available at the

end of the screening period and before initiation of treatment. The pathological review will be centralized nationally in each participating country in their national reference laboratories. The review will be done without knowledge of patient outcome and will comprise the confirmation of the diagnosis of MZL including specification of the MZL sub-type. Preferably, all the requested tumor paraffin embedded blocks from the formalin fixed sample (that was used for diagnosis) will be sent to one of the Pathology Reference Centers named in Appendix J. If this is not possible at least 10 unstained slides should be sent. As part of the central pathological review also the MYD88 mutation will be assessed. Furthermore, PD-L1 expression of lymphoma cells will be assessed by a validated method. The block remains at the central reference pathologist if patient gave his informed consent for that. The central reference pathologist will send the reference pathology report to the study site and the local pathologist that submitted the case for review. Histopathology central review process has become in the last years a common and prerequisite procedure for clinical trials in the field of lymphomas. It requires both a histopathological and immunohistochemical approach using an appropriate panel of antibodies according to the morphological pattern and, in some instances, further molecular or genetic analysis.

9.1.2 Tumor and Response Evaluation

All measurable disease must be documented at baseline and re-assessed according to assessment schedule provided in Appendix A. Initial CT/MRI scans used for screening evaluation should not be older than 6 weeks before start of treatment.

Response assessments will be performed by the investigator, based on physical examinations, CT/MRI scans, hematology, laboratory results, and bone marrow examinations, through use of Response Criteria for nodal, extranodal and splenic MZL (see Appendix D-F). CT scans (with contrast) should include chest, abdomen, and pelvis scans; CT scans of the neck should be included if clinically indicated (i.e., if evidence of disease on physical examination) and must be followed throughout the trial if there is disease involvement at baseline. MRIs of the chest, abdomen, and pelvis with a non-contrast CT scan of the chest may be used in patients for whom CT scans with contrast are contraindicated (i.e., patients with contrast allergy or impaired renal clearance). If MRI is used at screening, then MRI should be used throughout the study (**same method during the entire study**). In addition, the CT portion of a combined FDG-PET/CT scan may be used and collected with resolution sufficient to allow accurate and consistent comparison of target lesion measurements with subsequent CT scans. Use of FDG-PET/CT when clinically indicated and must be conducted always beforehand Pembrolizumab administration. Any time the investigator suspects disease progression, a full tumor

assessment must be performed, including a CT scan (limited to areas of prior involvement if required by local authorities).

In case of several lesions, the 6 largest ones should be measured and used as baseline value (if possible, the lesions should be from disparate regions of the body and should include mediastinal and retroperitoneal areas of disease whenever these sites are involved). If only a splenomegaly has been diagnosed, the spleen should also be measured by ultrasound so that the spleen can be monitored by ultrasound only to avoid unnecessary radiation.

In patients with gastric extranodal MZL, the initial staging should include a gastroduodenal endoscopy with multiple biopsies from the stomach, duodenum, gastroesophageal junction, and any site that seems abnormal and must not be older than 12 weeks before start of treatment. If any disease sites are identified in this manner at screening, a subsequent gastroduodenal endoscopy and biopsy are required to confirm a CR. In addition, if other sites are involved at baseline, they should be appropriately staged at baseline and re-evaluated during follow-up. For response evaluation endoscopy should be performed at C10D1 and at the end of treatment. H. pylori status must be evaluated. Endoscopic ultrasound to evaluate the regional lymph nodes and gastric wall infiltration should be performed.

In patients with non-gastric extranodal MZL, the initial staging should be adapted to the affected site as follows and according to local practice:

- Small intestine (immunoproliferative small intestinal disease, IPSID): Campylobacter Jejuni search in the tumor biopsy by polymerase chain reaction (PCR), immunohistochemistry or in situ hybridization may be carried out.
- Large intestine: colonoscopy.
- Lung: Bronchoscopy + bronchoalveolar lavage.
- Salivary glands: Ear/nose/throat examination and ultrasound. To eliminate association with Sjögren syndrome anti-SSA or anti-SSB antibodies should be investigated.
- Thyroid: echography ± computer tomography (CT) scan of the neck and thyroid function tests.
- Ocular adnexa: MRI (or CT scan) and ophthalmologic examination. Chlamydia psittaci in the tumor biopsy and blood mononuclear cells by PCR may be considered.
- Breast: mammography and MRI (or CT scan).
- Skin: Borrelia Burgdorferi in the tumor biopsy by PCR (in endemic areas) may be considered.

For all patients with extranodal MZL the MALT-IPI should be determined. It is the decision of the investigator to conduct a FDG-PET-CT. Investigations must not be older than 12 weeks before start of treatment. If any disease sites are identified in this manner at screening, a subsequent investigation is required to confirm a CR. For response evaluation investigations should be performed at C10D1 and at the end of treatment.

9.1.3 Bone marrow examinations

Bone marrow examinations should include a biopsy for morphology and an aspirate for local hematology (optional, if part of standard of care at site). Bone marrow examinations are required at screening for staging purposes in all patients (CR definition requires clearing of a previously infiltrated bone marrow) and must not be older than 12 weeks before start of treatment. If there was bone marrow infiltration at screening, then a subsequent bone marrow biopsy at the completion of cycle 9 is required for clinical response evaluation for all patients who may have achieved a CR. In patients with a PR and continued bone marrow involvement, a subsequent bone marrow examination may be required to confirm a CR at a later time point. An additional bone marrow aspirate may be done if that is standard of care at the site.

9.1.4 Demographic and medical history

Demographic data will include year of birth, gender and ethnic origin.

The investigator or designee will collect a complete medical and surgical history from 5 years before the screening through to the time of informed consent. Medical history will include information on the subject's concurrent medical conditions.

Relevant medical history, including previous chemotherapy/immunotherapy or radiotherapy, antecedent hematologic or oncologic disease, other diseases/symptoms such as fatigue, bleeding, and infection (only ongoing events) will be collected. Lymphoma history must date back to the initial diagnosis and any response duration must be recorded. Additionally the Ann Arbor Stage (Appendix G) will be determined.

9.1.5 Physical Examination

A complete physical examination should include an evaluation of head, eye, ear, nose, and throat and the cardiovascular, dermatological, musculoskeletal, respiratory, gastrointestinal, and neurological systems. As part of tumor assessment, physical examinations should also include the evaluation of the presence and degree of enlarged lymph nodes, hepatomegaly, and splenomegaly. At screening a complete physical examination will be performed. At the other timepoints physical examination should only include systems of most clinical relevance.

9.1.6 B Symptoms

At least the following B Symptoms have to be assessed: fever, night sweats and weight loss (unintentional loss of weight; e.g. more than 10% of body weight within the last 6 months).

9.1.7 Vital Signs

The assessment of vital signs must include height (only screening), weight, blood pressure, pulse and temperature.

9.1.8 ECOG

The ECOG Performance Status is one of two widely used methods to assess the functional status of a patient. The scale for evaluation is shown in appendix H.

9.1.9 Electrocardiograms

A 12-lead ECG and an echocardiography is required at screening and when clinically indicated. ECGs for each patient should be obtained from the same machine whenever possible, echocardiogram to measure LVEF

9.1.10 Laboratory Assessments

During treatment laboratory tests prior to each infusion may be performed either the day before or on the planned day of infusion. For dosing criteria, see Section 8.3.

Laboratory assessments will include the following:

- Hematology (hemoglobin, hematocrit, platelet count, red blood cell (RBC) count, white blood cell count, and percent or absolute differential count [total neutrophils, segmented neutrophils, banded neutrophils, eosinophils, lymphocytes, monocytes, basophils, malignant lymphocytes (e.g., villous lymphocytes in splenic MZL), other cells])
- Serum chemistries (sodium, potassium, chloride, bicarbonate, BUN, creatinine, calcium, magnesium, total bilirubin, total protein, albumin, CRP, LDH, ALT, AST, GGT, alkaline phosphatase, uric acid, glucose, BUN/creatinine ratio, lipase, amylase and β 2 microglobulin (β 2 microglobulin required only at screening). Phosphate, total cholesterol, LDL and triglycerides will be determined at Screening, on Day 1 of every 2nd cycle (2, 4, 6 etc.) and at the EOT visit. On these days patients must be fasting prior to sampling according to local standards. If a patient cannot adhere to fasting requirements, the evaluation of lipid-panels including triglycerides is considered not feasible.
- Quantitative immunoglobulins (IgG, IgA, and IgM)

- Serum electrophoresis (albumin, alpha 1, alpha 2, beta, gamma), relative and absolute determination of M protein if present. If M protein is present, immunofixation for detection of Ig subtype (IgG, IgA, IgM, IgD, light-chain kappa or lambda)
- Thyroid hormones: T3, T4, TSH
- Urine analysis: In a fresh sample of midstream urine, a dipstick testing for proteinuria is required (and microscopy including protein, specific gravity, glucose and blood).
- Urine Protein to Creatinine Ratio (UPCR) measurement.
- GFR calculation according to MDRD abbreviated formula
- Leukocyte immunophenotyping (FACS) PB and Bone Marrow Aspirate; Mandatory CD5, CD10, CD19, CD20, CD23, CD27, CD43, FMC7, kappa/lambda light chains.
- Coagulation (PTT or aPTT, prothrombin time, INR)
- Pregnancy test: All women of childbearing potential (including those who have had a tubal ligation) will have a pregnancy test at screening. WOCBP should only be included after a negative highly sensitive urine or serum pregnancy test. Following initiation of treatment, pregnancy testing will be performed whenever an expected menstrual cycle is missed or when pregnancy is otherwise suspected; at the time points specified in the Schedule of Activities and may be performed more frequently if required by local legislation. If a urine pregnancy test is positive, dosing will be delayed until the patient's status is determined by a serum pregnancy test.
- Viral serology and detection: Hepatitis B (HBsAg and total HBcAb and HBSAb) HBV DNA should be monitored every 4 weeks by real-time PCR with a limit of quantification of at least 29 IU/mL until at least 1 year after the last treatment cycle in patients who are HBsAg negative and HBcAb positive. If a patient is HBsAg negative and HBcAb positive during screening, additional serology for hepatitis B surface antibody (HBsAb) is required prior to Day 1 of Cycle 1. HCV antibody (also HCV RNA by PCR in a local laboratory if the patient is HCV antibody positive).

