Eligibility Criteria	
Others:
 
 • Age \geq 18 years • Life expectancy $>$3 months. • Meet the following pretreatment laboratory criteria at the Screening visit conducted within 28 days of study enrollment (unless due to underlying lymphoma): 
 – Baseline platelet count $\geq 75 \times 10^9/L$ (if not due to BM infiltration by the lymphoma), absolute neutrophil count $\geq 1.5 \times 10^9/L$ – Hemoglobin ≥ 9.0 g/dL or ≥ 5.6 mmol/L (Criteria must be met without erythropoietin dependency and without packed red blood cell (pRBC) transfusion within last 2 weeks) – International Normalized Ratio (INR) or Prothrombin Time (PT): $\leq 1.5 \times$ ULN unless subject is receiving anticoagulant therapy as long as PT or PTT is within therapeutic range of intended use of anticoagulants – Activated Partial Thromboplastin Time (aPTT): $\leq 1.5 \times$ ULN unless subject is receiving anticoagulant therapy as long as PT or PTT is within therapeutic range of intended use of anticoagulants – ASAT (SGOT): $\leq 2,5$ times the upper limit of institutional laboratory normal value or ≤ 5 times the upper limit of institutional laboratory normal value in subjects with lymphoma in the liver – ALAT (SGPT): $\leq 2,5$ times the upper limit of institutional laboratory normal value or ≤ 5 times the upper limit of institutional laboratory normal value in subjects with lymphoma in the liver – Serum total bilirubin: $\leq 1.5 \times$ ULN OR Direct bilirubin \leq ULN for subjects with total bilirubin levels > 1.5 ULN (unless clearly related to the disease) – Serum creatinine $\leq 1.5 \times$ ULN OR ≥ 60 mL/min GFR or CrCl for subjects with creatinine levels $> 1.5 \times$ institutional ULN – Negative HIV antibody – Patients with occult or prior HBV infection (defined as negative HBsAg and positive total HBcAb) may be included if HBV DNA is undetectable, provided that they are willing to undergo monthly DNA testing. Patients who have protective titers of HBSAb after vaccination or prior but cured hepatitis B are eligible – Patients positive for HCV antibody are eligible only if PCR is negative for HCV RNA – For women of child-bearing potential only: Serum or urine β-HCG must be negative during screening and at study enrolment visit. • Premenopausal fertile females must agree to use a highly effective method of birth control for the duration of the therapy up to 12 months after the last dose of Rituximab and through 4 months after the last dose of pembrolizumab. A

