- H. pylori-negative disease de novo or following or being not eligible for local therapy (i.e., surgery, radiotherapy or antibiotics) or after systemic therapy.
- H. pylori-positive disease that has remained stable, progressed, or relapsed following antibiotic therapy

Others:

- Age \geq 18 years
- Life expectancy > 3 months
- Meet the following pretreatment laboratory criteria at the Screening visit conducted within 28 days of study enrollment (unless due to underlying lymphoma):
 - Baseline platelet count \geq 75 $\times 10^9$ /L (if not due to BM infiltration by the lymphoma), absolute neutrophil count \geq 1.5 $\times 10^9$ /L.
 - Hemoglobin \geq 9.0 g/dL or \geq 5.6 mmol/L (Criteria must be met without erythropoietin dependency and without packed red blood cell (pRBC) transfusion within last 2 weeks)
 - International Normalized Ratio (INR) or Prothrombin Time (PT): \leq 1.5 \times ULN unless subject is receiving anticoagulant therapy as long as PT or PTT is within therapeutic range of intended use of anticoagulants

- Activated Partial Thromboplastin Time (aPTT): $\leq 1.5 \times \text{ULN}$ unless subject is receiving anticoagulant therapy as long as PT or PTT is within therapeutic range of intended use of anticoagulants
- ASAT (SGOT): $\leq 2,5$ times the upper limit of institutional laboratory normal value or ≤ 5 times the upper limit of institutional laboratory normal value in subjects with lymphoma in the liver
- ALAT (SGPT): $\leq 2,5$ times the upper limit of institutional laboratory normal value or ≤ 5 times the upper limit of institutional laboratory normal value in subjects with lymphoma in the liver
- Serum total bilirubin: $\leq 1.5 \times \text{ULN}$ OR Direct bilirubin $\leq \text{ULN}$ for subjects with total bilirubin levels $> 1.5 \text{ ULN}$ (unless clearly related to the disease)
- Serum creatinine $\leq 1.5 \times \text{ULN}$ OR $\geq 60 \text{ mL/min GFR}$ or CrCl for subjects with creatinine levels $> 1.5 \times \text{institutional ULN}$
- Negative HIV antibody
- Patients with occult or prior HBV infection (defined as negative HBsAg and positive total HBcAb) may be included if HBV DNA is undetectable, provided that they are willing to undergo monthly DNA testing. Patients who have protective titers of HBSAb after vaccination or prior but cured hepatitis B are eligible.
- Patients positive for HCV antibody are eligible only if PCR is negative for HCV RNA.

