Patients who complete Cycle 9 will be asked to return to the clinic within 4–6 weeks after Cycle 9 Day 1 for C10D1 visit. Patients who discontinued treatment early will be asked to return to the clinic for Early Termination Visit. An early termination visit should occur within 4–8 weeks after last dose (in case of early termination due to adverse event) or within 2–8 weeks after last dose (in case of early termination due to clinical disease progression). Please see the Study Flowcharts provided in Appendix A for schedules of assessments to be performed at the induction completion/early termination visit.

The following assessments should be performed on Cycle 10 Day 1 before receiving study drug or on Early Termination Visit unless otherwise specified in the protocol:

- In patients with gastric extranodal MZL: Gastroduodenal endoscopy
- Tumor Assessment: by CT/PET-CT/MRI and/or Bone Marrow aspirate and biopsy and/or Immunophenotyping PB and BM
- Complete physical examination, including vital signs
- ECOG Performance Status
- Laboratory:
 - Quantitative Immunglobulins (IgA, IgG, IgM)
 - Serum Protein Immunofixation if initially positive for monoclonal Ig

- Leukocyte immunophenotyping (FACS) PB (and Bone Marrow Aspirate);
- Hematology
- Serum Chemistry and electrophoresis
- Coagulation
- HBV DNA PCR in patients who are HBsAg negative and HBcAb positive
- Urinalysis (dipstick). Microscopy as clinically indicated
- Urine Protein to Creatinine Ratio (UPCR) measurement when clinically indicated
- GFR
- Women of childbearing potential: negative urine pregnancy test
- 12-lead ECG and an echocardiography when clinically indicated
- Safety assessment (see Section 8.3 and 11).
- Concomitant medication review. Please note: contrast media does not need to be recorded as concomitant medication unless there is an AE related to its administration (e.g. allergic reaction).
- In case of Early Termination Visit: new anti-lymphoma treatment

Please see the Study Flowcharts provided in Appendix A for schedules of assessments to be performed during Treatment phases.

Patients with at least SD will continue study treatment as specified above until end of cycle 18 or until PD is determined.

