^h Phosphate, total cholesterol, LDL and triglycerides will be determined at Screening, on Day 1 of every 2nd cycle (2, 4, 6 etc.) and at the EOT visit. On these days patients must be fasting prior to sampling according to local standards. If a patient cannot adhere to fasting requirements, the evaluation of lipid-panels including triglycerides is considered not feasible.

ⁱ At Screening in a fresh sample of midstream urine, a dipstick testing for proteinuria is required and microscopy including protein, specific gravity, glucose and blood. For further urine testing only dipstick, microscopy as clinically indicated

^j PB and bone marrow aspirate will be taken for the assessment of circulating lymphoma cells: mandatory: CD5, CD10, CD19, CD20, CD23, CD27, CD43, FMC7, kappa/lambda light chains.

^k an additional biopsy is done as part of the standard of care at the time of relapse or transformation, a tissue sample will be collected at that time.

^l B-Symptoms on Day 1 of each third cycle (i.e. on Day 1 of Cycles 1, 4, 7, 10, 13 and 17)

^m TSH is assessed before each treatment cycle, T3 and T4 only in case of laboratory abnormalities.

Follow-up – Phase for patients who have CR, PR or SD at the EOT visit

After last treatment cycle or after early termination	Follow-up Year 1 + 2 (every 3 months ± 14 days)								Follow-up Year 3 - 5 (every 6 months ± 14 days)						At the end of study or time of progression
	FU1	FU2	FU3	FU4	FU5	FU6	FU7	FU8	FU9	FU10	FU11	FU12	FU13	FU14	
Physical examination ^a	X	X	X	X	X	X	X	X	X	X	X	X	X	X	X
ECOG Performance Status	X	X	X	X	X	X	X	X	X	X	X	X	X	X	X
B symptoms	X	X	X	X	X	X	X	X	X	X	X	X	X	X	X
Pregnancy test	X														
Hematology	X	X	X	X	X	X	X	X	X	X	X	X	X	X	X
Serum chemistry ^b	X	X	X	X	X	X	X	X	X	X	X	X	X	X	X
Urine analysis ^c		X		X		X		X		X		X		X	X
HBV DNA PCR ^d	(X)	(X)	(X)	(X)											
New anti-lymphoma treatment ^e	X	X	X	X	X	X	X	X	X	X	X	X	X	X	X
Survival follow-up ^e	X	X	X	X	X	X	X	X	X	X	X	X	X	X	X
CT/MRI scan and tumor assessment (if initially positive)		X		X		X		X		X		X		X	X
Gastroduodenal endoscopy ^f		X		X		X		X		X		X		X	X
Leukocyte immunophenotyping (FACS) ^g		X		X		X		X		X					X
Quantitative immunoglobulins (IgA, IgG, IgM)		X		X		X		X		X					X
Serum protein immunofixation (if initially positive)		X		X		X		X		X					X
Bone marrow aspirate and biopsy ^h															X
Tumor tissue sample at time of relapse															(X) ⁱ
Adverse events ^j	X	X													
QoL questionnaire (FACT-Lym)				X				X		X		X		X	X

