Biological Material for Biobank (optional)															X (at progress)

Follow-up – Phase (continued)

CT=computed tomography; ECOG=Eastern Cooperative Oncology Group; FACS=fluorescence-activated cell sorter; HBV=hepatitis B virus; SAE=serious adverse event.

(x)=conditional/optional; refer to footnote for details.

^a The physical examination should only include systems of most clinical relevance.

^b Without Phosphate, total cholesterol, LDL and triglycerides

^c For further urine testing only dipstick, microscopy as clinically indicated

^d Only if clinically indicated. HBV DNA levels will be measured by real-time PCR using an assay with a sensitivity of at least 10 IU/mL.

^e **Patients with disease progression will be followed for new anti-lymphoma treatment and survival twice per year until the end of the study.**

^f In patients with gastric extranodal MZL. If clinically indicated it may be performed even more often. If there were no disease sites detectable at the last investigation, endoscopy should be performed every 6 months in year 1 to 2, and then once a year in year 3, 4 and 5 of follow-up. In the case of persistent disease sites endoscopy should be performed every three months until negativity.

^g A blood sample will be taken for the assessment of circulating lymphoma cells: mandatory: CD5, CD10, CD19, CD23, CD27, CD43, FMC7, kappa/lambda light chains

^h If initially positive or clinically indicated or in the case of progression

ⁱ If an additional biopsy is done as part of the standard of care at the time of relapse or transformation, a tissue sample will be collected at that time.

^j All AEs will be recorded up to 110 days after the last dose of study drug, study drug–related SAEs will be recorded indefinitely (even if the study has been closed).

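### After end of treatment, HBV DNA testing for HBsAg-negative/HBcAb-positive patients is 4-weekly in Protocol 9.1.10 but conditional and 3-monthly in the follow-up flowchart (internal inconsistency, minor)

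*Protocol*

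**What the plan says.** **Laboratory section.** Protocol 9.1.10 states: "HBV DNA should be monitored every 4 weeks by real-time PCR with a limit of quantification of at least 29 IU/mL" and, in the same sentence, "until at least 1 year after the last treatment cycle in patients who are HBsAg negative and HBcAb positive". It makes no exception for clinical indication or for progression.

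**During treatment and at its end.** Sections 9.3 and 9.4 and the treatment flowchart list "HBV DNA PCR in patients who are HBsAg negative and HBcAb positive" on Day 1 of each cycle from cycle 2, and at the end-of-treatment or early termination visit. These tests are not conditional on clinical indication.

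**Follow-up.** The second flowchart in Appendix A is headed "Phase for patients who have CR, PR or SD at the EOT visit". HBV DNA PCR appears there as a bracketed cross at FU1 to FU4, visits 3 months apart with a window of 14 days either side. The legend defines the bracketed mark as conditional or optional. Footnote d begins: "Only if clinically indicated. HBV DNA levels will be measured by real-time PCR". After progression, footnote e and section 9.5 (b) list only new anti-lymphoma therapy and survival.

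**Entry.** Under 7.1 and the synopsis, patients with occult or prior HBV infection "may be included if HBV DNA is undetectable, provided that they are willing to undergo monthly DNA testing". No duration is attached to that condition.

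**The concern.** The same patients have two different schedules after end of treatment. A site working from 9.1.10 would test every 4 weeks for a year. A site working from the follow-up flowchart would test at most every 3 months, and only if it saw a clinical reason. Sections 9.2 and 9.3 send sites to the Appendix A flowcharts for their schedules, and SAP 7.2 says patients without progression are observed according to the protocol's follow-up schedule. Using the flowchart alone is therefore a natural way to run the visits.

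Patient safety is what is at stake. Section 8.1.3.3 warns of hepatitis B reactivation under rituximab, including fatal fulminant hepatitis, and rituximab is given every second cycle through the planned 18 cycles. The year after the last cycle is the period 9.1.10 sets out to cover. There is also a reporting consequence: without knowing how many tests were done, a reader cannot tell whether no detected reactivation means negative tests or no tests.

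**Working it through.** The plan states no count of HBV DNA tests, so there is no figure to reproduce. The check compares scheduled counts in the year after the last cycle, for a patient who completes 18 cycles.

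**Inputs**
- Interval under 9.1.10: 4 weeks, for at least 1 year (52 weeks) after the last cycle.
- End-of-treatment visit: 4 weeks after Cycle 18 Day 1 (9.4 and treatment flowchart); test unconditional in this group.
- Follow-up slots: FU1 to FU4, every 3 months (about 13 weeks) ± 14 days, conditional. The chart is headed as running from the last treatment cycle or early termination, so FU4 falls at about 1 year.

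**Test counts**
- 9.1.10: 52 / 4 = 13 tests (weeks 4, 8, ..., 52 after Cycle 18 Day 1).
- Flowchart without progression: 1 + 0 = 1 to 1 + 4 = 5 tests.
- Shortfall: 13 − 5 = 8 to 13 − 1 = 12 tests.
- Progression before FU1: 1 test, shortfall 13 − 1 = 12.
- Progression after FU1, FU2 or FU3: 1 to 2, 1 to 3 or 1 to 4 tests.

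These are scheduled counts, not ceilings, because further tests may be done on indication.

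**Gaps between tests**
- No unconditional test after end of treatment (week 4) until the year is over. Counting the year from Cycle 18 Day 1: 52 − 4 = 48 weeks. Counting it from the end of cycle 18: (3 + 52) − 4 = 51 weeks.
- If every FU1 to FU4 test is done: about 13 weeks between visits, and up to 13 + 2 + 2 = 17 weeks when one visit is 14 days early and the next 14 days late.
- Interval under 9.1.10: 4 weeks.

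**Is the window still open?** SAP 2.1 gives 06 Dec 2024 as the end-of-treatment visit of the last patient enrolled. Assuming 18 cycles and a visit exactly 4 weeks after Cycle 18 Day 1:
- Cycle 18 Day 1: 06 Dec 2024 − 28 days = 08 Nov 2024.
- End of cycle 18: 08 Nov 2024 + 21 days = 29 Nov 2024.
- One year later: 08 to 29 Nov 2025, the end of the minimum window for that patient.

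**The case against.** The strongest case for leaving the text alone is that little depends on it. Recruitment stopped at 22 patients, the number in this serology group is unknown, and the window is closed or closing. Entry requires undetectable HBV DNA, and chronic active hepatitis B is excluded. Serum chemistry, which includes ALT and AST, is done at every follow-up visit for patients without progression. Section 8.1.3.3 calls for liver-expert consultation and monitoring by local standards. The treatment flowchart also notes that procedures without an asterisk follow routine or guidelines, and the HBV row has none. All of this stands. It lowers the risk and holds the severity at minor, but it does not make the two schedules agree.

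Footnote d could be read charitably, with HBcAb positivity itself counting as the clinical indication. But the protocol names this group wherever it means it (9.3, 9.4 and the treatment flowchart), and footnote d does not. Even on that reading the test would be 3-monthly. Nor does it help to count follow-up visits from the end-of-treatment visit, which would put FU4 just outside the year: the chart's heading counts from the last cycle or early termination.

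Some stronger readings are tempting but not supported:
- *The entry criterion independently demands monthly tests after treatment.* It gives no duration, and the next sentence admits patients with cured hepatitis B without a testing condition. It is supporting context only.
- *Section 9.5 contradicts 9.1.10 by leaving the test out.* Section 9.5 lists no laboratory tests at all, so its silence shows nothing by itself.
- *The assay limits conflict.* A sensitivity of at least 10 IU/mL in footnote d is compatible with the 29 IU/mL limit of quantification in 9.1.10.

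**Conclusion.** The inconsistency is real and confined to frequency and conditionality after end of treatment. For HBsAg-negative/HBcAb-positive patients, 9.1.10 implies about 13 tests in the year after the last cycle. The flowchart schedules 1 unconditional test and 0 to 4 conditional ones, and none after progression. No rule in the documents says which text governs.

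Severity is minor. The counts assume 18 completed cycles. After early termination the visit timing shifts, but there is still one unconditional test. A reader might infer that patients went untested or were put at risk; the documents do not show this. They do not say how many such patients were enrolled, what sites did in practice, or which text sites followed. The primary endpoint, sample size and error rate are not affected.

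**What to change.** First, list the HBsAg-negative/HBcAb-positive patients among the 22, with the date on which each passes one year after the last cycle.

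**If any is still inside the window,** reword follow-up footnote d in Appendix A along these lines: *For HBsAg-negative, HBcAb-positive patients: HBV DNA PCR at 4-week intervals for one year or longer after the final cycle (see 9.1.10), continuing after progression; for all other patients, on clinical indication only.* Write to the sites concerned. Under section 16.9 this needs Ethics Committee and Competent Authority approval or advice before implementation, unless overriding safety reasons apply. Compared with the flowchart's scheduled tests, it means 8 to 12 more blood draws per affected patient over a full year, but none beyond what 9.1.10 already asks for.

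**If none is,** no amendment is needed. Report the number of such patients and the HBV DNA tests recorded for each after end of treatment. The SAP already covers HBcAb and HBV DNA serology (7.1) and follow-up HBV DNA PCR (7.2), so the cost is one listing. It should carry a note that tests done between scheduled visits may not be in the database, so a low count could reflect incomplete capture rather than missing tests.
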